### **3.1.4. Safety Analysis Set**

The Safety Analysis Set includes all subjects who took at least 1 full dose of study drug. This is the primary analysis set for safety analyses.

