- [REDACTED]
- [REDACTED]
- [REDACTED]
- [REDACTED]
- [REDACTED]
- [REDACTED]

Pharmacokinetics: Presatovir concentrations in plasma will be analyzed for all subjects receiving presatovir treatment.

Statistical Methods: **Safety**
Safety analyses will be performed on all subjects who received at least 1 dose of IMP. Safety data will be listed by subject and summarized by treatment (active or placebo) using the number (percent) of subjects with events/abnormalities for categorical data and using descriptive statistics for continuous data.

Efficacy

The FAS will include all randomized subjects who take at least 1 full dose of study drug and have a RSV viral load greater than or equal to the lower limit of quantification (LLOQ) in the pre-dose Day 1/Baseline nasal sample, as determined by RT-qPCR conducted at the central lab. The subgroup analysis set includes subjects in the FAS whose duration of RSV symptoms prior to the first dose of study medication is \leq median. The FAS and the subgroup analysis set will be used for all summaries and analyses of the primary and secondary efficacy endpoints. All primary and other endpoints will be analyzed using 2-sided tests for treatment differences.

The primary efficacy analysis of time-weighted average change in RSV \log_{10} viral load from Day 1/Baseline through Day 7 will be performed on subjects included in the FAS and subjects included in the FAS subgroup with \leq median duration of symptoms prior to first dose of study medication. To test these 2 co-primary null hypotheses of no difference between the presatovir and placebo treatment groups in the time-weighted average change in RSV viral load, parametric analysis of covariance (ANCOVA) models with corresponding baseline RSV viral load as a continuous variable and stratification factors included as covariates will be used. Adjusted means and 95% confidence intervals (CIs) will be presented. The co-primary analyses will be controlled at an overall type I error rate at the 2-sided 0.05 level in which the alpha level for the overall population will be 0.04 and the alpha level for the subgroup population (subjects in the FAS with duration of RSV symptoms prior to first dose of study medication \leq median) will be 0.017, as determined by a grid search accounting for the known correlation of the populations.

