5.3. Dosage and Administration of Presatovir

Eligible subjects will receive presatovir administered as a 200-mg dose (4 x 50 mg tablets) on Day 1/Baseline, followed by daily 100-mg dose (2 x 50 mg tablets) on Days 2 through 14, or PTM once daily for a total of 14 days.

All IMP or PTM will be administered orally or via a NG tube if required. The entire dose must be taken within 1 hour. If administration through a NG tube is required, tablets may be crushed and dissolved in water. IMP should be dispensed with gloves. Subjects will remain in the clinic

for 30 minutes post-dose for observation. On any day, if vomiting occurs within 30 minutes after ingesting the last pill and pills or pill fragments are found in the vomitus, the subject may re-dose after contacting designated site staff. If another dose is administered, and site staff or home health agency nurses are present, the subject should be observed for an additional 30 minutes post-dose to record whether the dose was tolerated or if additional vomiting occurred. If no site staff or home health agency nursing staff are present during an approved re-dosing episode, follow-up is required 30 to 60 minutes after re-dosing to record tolerance to the re-dosing attempt as above. The subject may be re-dosed only once per day.

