7.2.2. Assessment of Severity

Severity should be recorded and graded according to the GSI Grading Scale for Severity of Adverse Events and Laboratory Abnormalities. For AEs or SAEs associated with laboratory abnormalities, the event should be graded on the basis of the clinical severity in the context of the underlying conditions; this may or may not be in agreement with the grading of the laboratory abnormality.

7.3. Investigator Requirements and Instructions for Reporting Adverse Events and Serious Adverse Events to Gilead

Requirements for collection prior to IMP initiation:

After informed consent, but prior to initiation of study medication, the following types of events should be reported on the case report form (eCRF): all SAEs and adverse events related to protocol-mandated procedures.

Adverse Events:

Following initiation of study medication, all AEs, regardless of cause or relationship, through the Day 28/End of Study visit must be reported to the CRF/eCRF database as instructed. All AEs should be followed up until resolution or until the adverse event is stable, if possible.

Gilead Sciences may request that certain AEs be followed beyond the protocol defined follow up period, as determined by the Medical Monitor.

Serious Adverse Events:

All SAEs, regardless of cause or relationship, that occurs after the subject first consents to participate in the study (ie, signing the informed consent) and throughout the duration of the study, including the protocol-required post treatment follow-up period, must be reported to the eCRF database and Gilead Drug Safety and Public Health (DSPH) as instructed. This also includes any SAEs resulting from protocol-associated procedures performed after informed consent is signed.

Any SAEs and deaths that occur, regardless of causality, should also be reported.

Investigators are not obligated to actively seek SAEs after the protocol defined follow up period (the Day 28/End of Study visit), however, if the investigator learns of any SAEs that occur after study participation has concluded and the event is deemed relevant to the use of IMP, he/she should promptly document and report the event to Gilead DSPH.

PPD

All AEs and SAEs will be recorded in the eCRF database within the timelines outlined in the eCRF completion guideline.

Electronic Serious Adverse Event (eSAE) Reporting Process:

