8.2.1.2. Safety

The primary analysis set for safety analyses is defined as all subjects who received at least a full dose of IMP.

All data collected during treatment will be included in the safety summaries.

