#### **7.1.5. Treatment-Emergent Adverse Events**

##### **7.1.5.1. Definition of Treatment-Emergent Adverse Events**

Treatment-emergent adverse events (TEAEs) are defined as 1 or both of the following:

- Any AEs with an onset date on or after the study drug start date up to the Day 28 visit, or up to 28 days if a subject withdraws early (prior to Day 28) from the study
- Any AEs leading to premature discontinuation of study drug

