#### 7.1.6. Summaries of Adverse Events and Deaths

Treatment-emergent (TE) AEs will be summarized based on the Safety Analysis Set.

The number and percentage of subjects who experienced at least 1 TEAE will be provided and summarized by SOC and PT, and treatment group. For other AEs described below, summaries will be provided by SOC and PT, and treatment group:

- TEAE by maximum severity
- TEAEs of Grade 3 or higher
- TEAEs of Grade 2 or higher
- All TE treatment-related AEs
- All TE treatment-related AEs by maximum severity
- TE treatment-related AEs of Grade 3 or higher
- TE treatment-related AEs of Grade 2 or higher
- All TE SAEs
- All TE treatment-related SAEs
- All TEAEs leading to premature discontinuation of study drug

- All TEAEs leading to premature discontinuation of study (main study portion)
- All AEs leading to death (ie, outcome of death)

A brief, high-level summary of AEs described above will be provided by treatment group and by the number and percentage of subjects who experienced the above AEs. All deaths observed in the study (with the death date on or after the study drug start date up to Day 28) will be also included in this summary.

Multiple events will be counted only once per subject in each summary. Adverse events will be summarized and listed first in alphabetic order of SOC and HLT within each SOC (if applicable), and then by PT in descending order of total frequency within each SOC. For summaries by severity grade, the most severe grade will be used for those AEs that occurred more than once in an individual subject during the study.

In addition to the above summary tables, all TEAEs, TE treatment-related AEs, and TE SAE will be summarized by PT only, in descending order of total frequency.

In addition, data listings will be provided for the following:

- All AEs, indicating whether the event is treatment emergent
- All AEs of Grade 3 or higher
- All AEs of Grade 2 or higher
- SAEs
- Deaths
- All AEs leading to death (ie, outcome of death)
- AEs leading to premature discontinuation of study drug
- AEs leading to premature discontinuation of study (main study portion)

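### The Safety Analysis Set requires a full dose, so an exposed subject who never completes any dose is left out of the safety tables and the AE/SAE listings

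*SAP*

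**What the plan says.** Three places define who is analysed for safety:

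- SAP 3.1.4: "The Safety Analysis Set includes all subjects who took at least 1 full dose of study drug".
- Protocol 8.2.1.2: "The primary analysis set for safety analyses is defined as all subjects who received at least a full dose of IMP".
- Protocol synopsis, Statistical Methods, Safety: "Safety analyses will be performed on all subjects who received at least 1 dose of IMP".

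The first dose has several parts. Protocol 5.3 says: "Eligible subjects will receive presatovir administered as a 200-mg dose (4 x 50 mg tablets) on Day 1/Baseline", and "The entire dose must be taken within 1 hour". Tablets may also be crushed and given by NG tube. Doses on Days 2 through 14 are two tablets. The synopsis gives placebo the same tablet counts.

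The adverse event rules carry no full-dose condition. Protocol 7.3 says: "Following initiation of study medication, all AEs, regardless of cause or relationship, through the Day 28/End of Study visit must be reported". SAP 7.1.5.1 counts an event as treatment-emergent if it starts on or after the study drug start date (up to Day 28), and also counts "Any AEs leading to premature discontinuation of study drug".

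The outputs do carry the condition, through the analysis set. SAP 7.1.6 says: "Treatment-emergent (TE) AEs will be summarized based on the Safety Analysis Set".

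**The concern.** A safety population should contain everyone who was exposed. Here, entry depends on completing a dose, and one plausible reason for not completing it is a reaction to it. Any loss would therefore be selective, because the subjects removed would tend to be those with acute intolerance. Safety and tolerability are stated objectives. The planned DMC safety review was also cancelled (SAP 2.1 and 7.7), so the final safety outputs carry more of the weight. Listing 16.2.7.5.1, which is meant to show adverse events leading to stopping study drug, would omit this case.

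**Working it through.** The plan states no figure on this point, so the check is mainly a trace of one subject through the documents.

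**1. Who is left out.** The rule asks for at least one full dose at any time, not a full first dose. A subject is lost only if both of these hold:

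- some, but not all, of the Day 1 dose was taken; and
- no complete dose was taken on any of the 13 later dosing days.

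**2. What happens to that subject's adverse event.**

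| Step | Source | Result |
|---|---|---|
| Is it collected? | Protocol 7.3 | Yes, from initiation of study medication |
| Is it treatment-emergent? | SAP 7.1.5.1 | Yes: onset on or after drug start; if it stopped treatment, under the second limb as well |
| Is it in the safety tables? | SAP 7.1.6 and 13.1 | No: every 15.11.x table uses the Safety Analysis Set |
| Is it in the AE/SAE listings? | SAP 13.3 | No: 16.2.7.1, 16.2.7.2.2, 16.2.7.3, 16.2.7.4.1, 16.2.7.4.2, 16.2.7.5.1 and 16.2.7.5.2 all use the Safety Analysis Set |
| Is there an exception? | SAP 13.3 | Deaths only (16.2.7.2.1, All Randomized) |

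SAP Section 3 confines by-subject listings to the relevant analysis set, and no SAP text adds a partially dosed subject back. Protocol 8.6 says that all safety data are to be listed, so the assignments in SAP 13.3 do not deliver what the protocol commits to.

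**3. Where the subject remains visible.** SAP 13.3 puts these listings on the All Randomized set: subject profiles (16.2.1.1), disposition (16.2.1.3), exclusions from analysis sets (16.2.3.1), drug administration (16.2.5.1) and premature discontinuation of study drug (16.2.5.2). None of them is an adverse event listing.

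**4. Size per case.** Planned randomization is 60 subjects at 2:1 (51 evaluable / 0.85 = 60). That gives 60 × 2/3 = 40 on presatovir and 60 × 1/3 = 20 on placebo. Let k be the number of partial-dose subjects with an intolerance event, and x the number of other presatovir subjects with such an event. The value of k is an assumption, since the documents give no rate.

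- Reported rate under the current rule: x / (40 − k)
- Rate among all exposed: (x + k) / 40

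| k | x = 0 | x = 2 | x = 4 |
|---|---|---|---|
| 1 | 0.0% vs 2.5% | 5.1% vs 7.5% | 10.3% vs 12.5% |
| 2 | 0.0% vs 5.0% | 5.3% vs 10.0% | 10.5% vs 15.0% |
| 3 | 0.0% vs 7.5% | 5.4% vs 12.5% | 10.8% vs 17.5% |

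Each cell gives the current rule first and all exposed second. On placebo with no other events, one case turns 1/20 (5.0%) into 0/19. If k = 0, nothing changes.

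**5. Knock-on to PK.** SAP 3.1.5 and Protocol 8.2.1.3 draw the PK Analysis Set from the Safety Analysis Set. Widening the safety set alone would let a partial-dose subject with a 2 to 4 hour Day 1 sample into concentration summaries meant for the 200-mg dose.

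**The case against.** The strongest reply is that the case is rare and would be disclosed anyway. One hour is a ceiling, not a staggered schedule. Drug-derived radioactivity peaked at 2 hours in the mass-balance study (Protocol 1.2.4.2), so most systemic reactions would be expected after the last tablet. Protocol 1.3 reports no SAE, no Grade 3 or higher AE and no discontinuation for an AE among presatovir-treated subjects in the completed studies. The operative protocol section and the SAP agree, and the synopsis wording can be read as shorthand for the protocol-defined dose.

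Much of this stands. The frequency may be zero, although the completed studies enrolled healthy adults, not lung transplant recipients with an acute infection. The synopsis difference is one of wording to be aligned, not proof of two intended populations. Rarity and disclosure elsewhere still do not put the event into the adverse event tables or listings.

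A reader might infer more than the documents support:

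- **That anyone who stops part-way through the first dose is lost.** One later complete dose brings the subject back. A completed re-dose after vomiting would appear to do so too, although full dose is not defined for that situation.
- **That the subject vanishes from the report.** The All Randomized listings show otherwise, SAP 3.1 requires exclusions and their reasons to be summarized and listed, and SAE reporting does not depend on the analysis set.
- **That the safety comparison is biased in favour of presatovir.** That needs a case to occur on presatovir. A case on placebo would move the comparison the other way.

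**Conclusion.** The point holds in a limited form. As written, the Safety Analysis Set would omit an exposed subject who never completes any dose from all 15.11.x tables and from all AE/SAE listings other than Deaths. This is so even though the event is collected and counts as treatment-emergent, and it conflicts with Protocol 8.6. The size depends on a case occurring: 2.5 percentage points per presatovir case and 5 per placebo case when there are no other events, on the planned arms of 40 and 20. For the intolerance events themselves the absolute rate is understated. The effect on the difference between arms depends on where the cases fall. The change is worth making because any loss would be selective for tolerability and the repair is cheap.

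**What to change.** In the protocol synopsis, Protocol 8.2.1.2 and SAP 3.1.4, define the Safety Analysis Set as all subjects who took any amount of study drug, meaning at least one tablet or any part of an NG-tube dose. The assignments in SAP 13.1 and 13.3 can then stay as they are. Leave the FAS definition unchanged. In SAP 3.1.5 and Protocol 8.2.1.3, either keep the PK Analysis Set to subjects with at least one full dose or flag partial-dose samples, so that the PK summaries do not change.

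The cost is a small wording change in both documents and a separate condition for the PK set. The protocol edit goes through the IRB/IEC step in Protocol 9.2.1. SAP 3.1 fixes set membership before the blind is broken, so the change can be made blind. No efficacy analysis is affected, and if no subject took only a partial dose, no result changes.

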### **3.1.5. Pharmacokinetic Analysis Set**

The Pharmacokinetic (PK) Analysis Set includes all subjects in the Safety Analysis Set who have evaluable on-study PK measurements. This is the primary analysis set for all PK analyses.

## **3.2. Subject Grouping**

For analyses based on the FAS and PP Analysis Set, subjects will be grouped according to the treatment to which they were randomized. For analyses based on the Safety Analysis Set, subjects will be grouped according to the actual treatment received. The actual treatment received will differ from the randomized treatment only when their actual treatment differs from randomized treatment for the entire treatment duration. For the PK Analysis Set, subjects will be grouped according to the actual treatment they received.

### 3.3. Strata and Covariates

Subjects will be randomly assigned to treatment groups via the interactive web response system (IWRS) in a 2:1 ratio using a stratified randomization schedule. Stratification will be based on the following parameters:

- Treatment of RSV infection (yes or no) with ribavirin (oral, intravenous, or aerosolized)
- Use of palivizumab or IVIG (yes or no)

If there are discrepancies in stratification factor values between the IWRS and the clinical database, the values recorded in the clinical database will be used for analyses.

Efficacy endpoints will be evaluated using stratification factors as covariates for analyses, as specified in Section 6. If there are a small number of subjects (eg,  $\leq 4$  subjects) within a stratum of the stratification factor, then the stratum will be collapsed with the adjacent stratum for the analysis.

For efficacy endpoints, the baseline value of the efficacy variables will be included as a covariate in the efficacy analysis model.

### 3.4. Examination of Subject Subgroups

The primary efficacy endpoint will be examined using the following subgroup:

- RSV type (RSV A or RSV B)

The safety endpoints will be examined using the following subgroups:

- Age ( $< 65$  years and  $\geq 65$  years)
- Sex (male and female)

### 3.5. Multiple Comparisons

In order to account for multiple hypothesis testing of the co-primary efficacy endpoints, an appropriate alpha allocation was numerically derived utilizing the inherent correlation between the test statistics (details provided in [Appendix 2](#)), which preserves the overall significance level of testing the primary endpoint at 0.05 (2-sided). Specifically, the alpha level for the overall FAS population will be 0.04 and the alpha level for the subgroup population (subjects in the FAS with duration of RSV symptoms prior to the date of the first dose of study medication  $\leq$  a median value of the distribution of RSV symptom duration in the overall FAS population) will be 0.017.

If the primary null hypothesis is rejected, then the following secondary endpoints will be tested sequentially, based upon the closed testing procedure [{Dmitrienko 2003}](#).

- Time-weighted average change in FLU-PRO score from Day 1/Baseline through Day 7

- Percent change from study baseline in FEV1% predicted value at Day 28/End of Study

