8.2. Analysis Conventions

8.2.1. Analysis Sets

8.2.1.1. Efficacy

The FAS will include all randomized subjects who take at least 1 full dose of study drug, and have an RSV viral load greater than or equal to the lower limit of quantification (LLOQ) of the RT-qPCR assay in the pre-dose Day 1/Baseline nasal sample, as determined by RT-qPCR at the central lab. The subgroup analysis set includes subjects who are in the FAS whose duration of RSV symptoms prior to first dose of study medication is \leq median. The FAS and the subgroup analysis set will be used as the primary analysis sets for all summaries and analyses of the primary and secondary efficacy endpoints.

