8.5. Efficacy Analysis

8.5.1. Primary Analysis

The primary endpoint is the time-weighted average change in nasal RSV viral load (\log_{10} copies/mL) from Day 1/Baseline through Day 7. The primary analysis will be performed on subjects included in the FAS and subjects included in the FAS with \leq median duration of symptoms prior to the first dose of study medication. To test these two co-primary null hypotheses of no difference between the presatovir and placebo treatment groups in the time-weighted average change in RSV viral load in the FAS and in the subgroup, parametric analysis of covariance (ANCOVA) models with corresponding baseline RSV viral load as a continuous variable and stratification factors included as covariates will be used. Adjusted means and 95% CIs will be provided. If stratification leads to small cell sizes, a modification to the stratification, which will be described in the SAP, will be implemented.

The co-primary analyses will be controlled at an overall type I error rate at the 2-sided 0.05 level in which the alpha level for the overall FAS population will be 0.04 and the alpha level for the subgroup population (subjects in the FAS with duration of RSV symptoms prior to first dose of study medication \leq median) will be 0.017, as determined by a grid search accounting for the known correlation of the populations.

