8.5.2. Secondary Analyses

The FAS analysis set will be used for all summaries and analyses of secondary endpoints. All secondary endpoints will be analyzed using 2-sided tests to compare treatment differences.

The time-weighted average change in FLU-PRO score from Day 1/Baseline through Day 7 will be analyzed using an ANCOVA model with the baseline FLU-PRO score value and stratification factors as covariates. Adjusted means and a 95% CI will be provided.

The percent change in FEV₁% predicted values from Day 1/Baseline through Day 28/End of Study will be analyzed using an ANCOVA model with study baseline FEV₁% predicted value and stratification factors as covariates. The percent change in FEV₁% predicted values will be calculated as the difference of FEV₁% predicted values at study baseline and Day 28/End of Study, divided by study baseline FEV₁% predicted value and multiplied by 100.

In order to account for multiple hypothesis testing across the primary and secondary endpoints, a family alpha spending rule will be used to control the Type 1 error rate of 0.05. The co-primary endpoint analyses will serve as the gatekeeper for the secondary analyses conducted within each population. If the co-primary null hypothesis is rejected, then the following secondary endpoints will be tested sequentially at the specified alpha-level within each population (ie, $\alpha = 0.04$ and/or $\alpha = 0.017$), respectively, based upon the closed testing procedure {[Dmitrienko et al 2003](#)}.

- Time-weighted average change in FLU-PRO score from Day 1/Baseline through Day 7
- Percent change from study baseline in FEV₁% predicted value at Day 28/End of Study

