### **6.2.2. Analysis Methods for Secondary Efficacy Endpoints**

The FAS analysis set will be used for all summaries and analyses of the secondary endpoints.

The treatment difference in the time-weighted average change in FLU-PRO score from Day 1/Baseline to Day 7 will be analyzed using an ANCOVA model with the baseline FLU-PRO score and stratification factors as covariates.

The treatment difference in the percent change from study baseline in FEV1 % predicted value at Day 28 will be analyzed using an ANCOVA model with the study baseline FEV1 % predicted value and stratification factors as covariates. The study baseline FEV1 % predicted value is defined as the lowest FEV1 % predicted value collected on or prior to the first dosing date if multiple non-missing numeric assessments exist. The data collected on eCRF will be used for the analyses.

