## Appendix 2. Alpha Allocation Approach

There are 2 test statistics in the study design, denoted by  $Z_k$  for  $k$ th population (1 = overall; 2 = subgroup population [including subjects who are in the FAS whose duration of RSV symptoms prior to the first dose of study medication is  $\leq$  median of the distribution of duration of RSV symptoms in the overall FAS population] with prevalence  $b_1$ ). Specifically,  $b_1 = 0.5$  for 50th percentile threshold.

For alpha spending across the 2 tests for the primary endpoint of time-weighted average change in viral load from baseline to Day 7, the following rules are implemented, where  $c_k$  denotes the rejection boundary for the  $k$ th population:

- Pre-fix rejection boundaries ( $c_1 = 2.054$ ) for the final analysis in the overall population

$\tilde{Z} = (Z_1, Z_2)$  is a vector of standardized test statistics that follow a multivariate normal distribution with mean  $\tilde{\mu} = (\mu_1, \mu_2)$ . For a very large clinical trial and assuming no prognostic or predictive effect of duration of RSV symptoms prior to the first dose on the primary endpoint, the variance-covariance matrix for the vector  $\tilde{Z}$  can be shown to be:

$$\Sigma = \begin{pmatrix} 1 & \sqrt{b_1} \\ \sqrt{b_1} & 1 \end{pmatrix}$$

Under the null hypothesis,  $\tilde{\mu} = (0, 0)$ . Given the above rules and the variance-covariance matrix  $\Sigma$ , the table below presents the rejection boundaries for the final analysis, which can be numerically calculated such that the overall type I error rate is maintained at the 2-sided 0.05 level.

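### The SAP does not say which co-primary rejection opens the secondary endpoints, in which population or at what alpha, and the protocol's own 0.04/0.017 chains do not guarantee 0.05 across endpoints

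*SAP*

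**What the plan says.** **Primary tests.** SAP 6.1.2 sets out two nulls for DAVG7: H01 in the FAS and H02 in the subgroup. SAP 3.5 states that "the alpha level for the overall FAS population will be 0.04". Protocol 8.5.1 says that the subgroup level "will be 0.017, as determined by a grid search accounting for the known correlation of the populations". SAP Appendix 2 derives this split for the two tests of the primary endpoint only.

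**Secondary tests, protocol.** Section 8.5.2 makes the co-primaries the gatekeeper within each population. After a rejection the secondaries are "tested sequentially at the specified alpha-level within each population", that is, at 0.04 and/or 0.017. The stated aim there and in the synopsis is a type I error of 0.05 across primary and secondary endpoints. On the populations for these endpoints, Section 8.2.1.1 agrees: "The FAS and the subgroup analysis set will be used as the primary analysis sets for all summaries and analyses of the primary and secondary". But 8.5.2 opens with a sentence that limits all secondary analyses to the FAS.

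**Secondary tests, SAP.** Section 3.5 has one gate sentence: "If the primary null hypothesis is rejected, then the following secondary endpoints will be tested sequentially, based upon the closed testing procedure". It gives no population and no level for the secondaries. Section 6.2.2 adds: "The FAS analysis set will be used for all summaries and analyses of the secondary endpoints". Section 3.1.2, by contrast, names both the FAS and the subgroup set as primary sets for efficacy analyses. The proposed table list (13.1) has subgroup tables for DAVG7 (15.9.1.2.1 and 15.9.1.2.2) but none for FLU-PRO or FEV1.

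**The concern.** There are two primary nulls, and the SAP conditions on one without saying which. The case that matters is a split result. If only the subgroup primary succeeds, the protocol's gate calls for FLU-PRO and FEV1 in the subgroup at 0.017. The SAP either opens FAS secondaries in the population where the primary failed, or opens nothing. The choice could then be made after the blind is broken, when the results are visible.

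The second issue is the level. The pair 0.04 and 0.017 sums to 0.057. It meets 0.05 only because the two tests concern the same endpoint in nested populations and are therefore correlated. Further down the chains, the two hypotheses at risk can be different endpoints, and that correlation weakens. The protocol nevertheless claims 0.05 across the whole set.

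**Working it through.** **Inputs**
- Levels 0.04 and 0.017; boundaries 2.054 and 2.379; subgroup prevalence 0.5, so correlation √0.5 = 0.7071 (SAP 3.5 and Appendix 2).
- Planned sizes 34 and 17 in the FAS, 17 and 9 in the subgroup (SAP 1.3).
- Between-endpoint correlation g: not in the documents. Assumed, and ranged from 0 to 1.
- False nulls are taken as always rejected (worst case).

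**Formula.** For two tests with boundaries c1 and c2 and correlation r:

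error = 1 − P(|Z1| ≤ c1 and |Z2| ≤ c2), with (Z1, Z2) bivariate normal.

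**Step 1: the plan's own figure.** At r = 0.7071, boundaries 2.054 and 2.379 give 0.04996; the rounded levels 0.04 and 0.017 give 0.0497. Solving for c2 with the FAS at 0.04 gives 2.3786 (p = 0.0174). With the planned sizes, r = √[(1/34 + 1/17)/(1/17 + 1/9)] = 0.7206 and the error is 0.0494. The co-primary split is sound.

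**Step 2: what each rule opens**

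| Primary result | Protocol 8.5.2 gate | SAP, if the gate is H01 | SAP, if either rejection suffices |
|---|---|---|---|
| FAS only | FAS secondaries at 0.04 | FAS secondaries, level unstated | FAS secondaries, level unstated |
| Subgroup only | Subgroup secondaries at 0.017 | Nothing | FAS secondaries, level unstated |
| Both | Both chains | FAS secondaries, level unstated | FAS secondaries, level unstated |

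With SAP 6.2.2 in force, neither reading runs the protocol's subgroup secondary tests.

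**Step 3: error under the either-rejection reading.** Take H02 false, H01 true and FAS FLU-PRO null. H01 (at 0.04) and FAS FLU-PRO are then both exposed, with correlation g.

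| Secondary alpha (assumed) | g = 0 | g = 0.5 |
|---|---|---|
| 0.017 | 0.0563 | 0.0534 |
| 0.04 | 1 − 0.96 × 0.96 = 0.0784 | 0.0732 |
| 0.05 | 1 − 0.96 × 0.95 = 0.0880 | 0.0821 |

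**Step 4: error under the protocol's two chains.** In a fixed sequence, a false rejection requires rejection of the first true null in that chain. The overall error is therefore the union probability for the first true null in each chain, at 0.04 and 0.017.
- Same endpoint in both chains (including the global null): r = 0.7071, error 0.0497.
- Different endpoints, for example FAS DAVG7 effect real, subgroup DAVG7 null and FAS FLU-PRO null: r = g × 0.7071.

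| g | 0 | 0.3 | 0.5 | 0.7 | 1 |
|---|---|---|---|---|---|
| Error | 0.0563 | 0.0558 | 0.0549 | 0.0534 | 0.0497 |

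At g = 0 this is 1 − 0.96 × 0.983 = 0.0563. The bound without any correlation assumption is 0.04 + 0.017 = 0.057. A simulation of 2 million draws agreed with these figures to within simulation error.

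**The case against.** Several points on the other side stand.

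- **The SAP did not invent the FAS-only rule.** Its sentence in 6.2.2 closely follows the opening of protocol 8.5.2. The contradiction begins in the protocol, and the SAP is also inconsistent with itself (3.1.2 against 6.2.2). The table list is headed as proposed, so missing titles are supporting evidence and not a decision rule.
- **A reader might infer that a subgroup-only win would open FAS secondary tests.** The text does not settle that. The gate is singular and SAP 6.1.2 lists H01 first in a sequence, so H01 alone may be meant. Only could is supported.
- **A reader might take 8.8% as the error of the SAP.** That figure needs the either-rejection reading, a secondary alpha of 0.05 that SAP 3.5 does not state, independent endpoints, certain rejection of H02, and a real subgroup effect with the FAS null exactly true. Because the subgroup is half of the FAS, the last condition implies a roughly equal and opposite effect in the other half. It is a ceiling.
- **The chain excess is small and conditional.** If each endpoint's null has the same status in both populations, the first true nulls are the same endpoint and the error is 0.0497.
- **SAP 3.5 claims 0.05 only for the primary endpoint.** The wider promise is the protocol's. Both documents cite a closed testing procedure, and a fully specified one would control the error. Fixed chains at 0.04 and 0.017 are not one unless cross-endpoint intersections receive tighter levels.
- **The text of SAP 6.5, on changes from the protocol's efficacy analyses, is blacked out.** It cannot be said that the departure was undocumented.

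What remains is that the visible text gives the secondary tests no defined trigger or level and conflicting populations.

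**Conclusion.** The point holds in two parts of unequal weight.

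1. **Gate and population.** SAP 3.5 and 6.2.2 do not implement the within-population gate of protocol 8.5.2, and both documents contradict themselves on the population. This rests on the text alone. If either rejection opens FAS secondaries at 0.04, the error could reach about 7.3-7.8% (g from 0.5 to 0), but only when the subgroup effect is real and the FAS null is true. This part should be settled before unblinding.
2. **Level across endpoints.** The protocol's chains do not guarantee the 0.05 it promises. The error is 0.053-0.056 for g from 0.7 to 0 when the first true nulls are different endpoints, with a bound of 0.057. This is a lesser matter and not a must-fix.

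A reader should not conclude that the co-primary split is faulty, or that the protocol's chains always exceed 0.05. The split reproduces, and the excess is absent under the global null.

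**What to change.** - In SAP 3.5 and 6.2.2, specify two chains, each opened only by its own primary. FAS: DAVG7 at 0.04, then FLU-PRO, then FEV1. Subgroup: DAVG7 at 0.017, then FLU-PRO, then FEV1. State the level of every test.
- Reconcile the FAS-only sentences in protocol 8.5.2 and SAP 6.2.2 with the within-population gate in protocol 8.5.2, with protocol 8.2.1.1 and with SAP 3.1.2. Editing the SAP alone would leave the protocol inconsistent.
- Add subgroup tables for FLU-PRO and FEV1 to SAP 13.1.
- Either use secondary levels that are valid across endpoints, or drop the claim of 0.05 control over the secondaries. One valid choice is 0.033 in the FAS and 0.010 in the subgroup: 0.033 + 0.017 = 0.050, 0.04 + 0.010 = 0.050 and 0.033 + 0.010 = 0.043, while the co-primary pair stays at 0.0497. An explicitly specified closed test would also serve.

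**Cost.** Wording in both documents and two tables; no change to design or data collection. The tighter levels cost secondary alpha: 0.007/0.04 = 17.5% of the FAS level and 0.007/0.017 = 41% of the subgroup level. The subgroup loss is the heavier one, with only 17 and 9 subjects planned there.
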